### 2) Objectives\*

This study is intended to study the effects of one-time acute dosing of a solid extract of *Passiflora incarnata*, also known as Passionflower, along with a 10 minute audio-guided mobile meditation on medical students after a didactic examination. Our hypothesis is that blood pressure levels and heart rates, as an assessment of sympathetic tone, will decrease significantly in response to both *Passiflora incarnata* and the meditation.

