**b) Inclusion and Exclusion Criteria\***

i) **Inclusion criteria** – all naturopathic medical students are invited to participate

(1) Participants must have a smartphone with access to the Headspace application and headphones to listen to the session

ii) **Exclusion criteria**

(1) Those taking hypertensive medication

(2) Those taking anti-anxiety medication, including MAOI medication

(3) Those taking blood-thinning medication

(4) Those who are pregnant

(5) Those who could be pregnant

(6) Those who will have surgery 2 weeks before the research date

(7) Those who are scheduled to have surgery 2 weeks after the research date

(8) Those who do not have a smartphone or access to Headspace application

(9) Those who have consumed caffeine, food/tyramine containing foods, stimulant medication, cold medicine, decongestant medicine, antihistamine medicine, cough suppressants, alcoholic beverages, or stimulant energy drinks within 2 hours before the study period.

iii) Interested participants will be contacted by phone or in-person by one of the investigators ([name] or [name]) and screened for exclusion criteria

iv) We aim for 70 subjects to participate but can complete the research with 45-60 subjects to achieve 80-90% power, respectively.

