**d) Procedures involved in the Human Research\***

i) This will be a randomized, double-blind, placebo controlled trial.

ii) Students will be randomized to Group I, II, or III before the study begins

UB HRP-503 TEMPLATE: Protocol

PROTOCOL TITLE: Investigating the short-term effects of *Passiflora incarnata* and mobile audio-guided meditation on blood pressure and heart rate in naturopathic medical students

PROTOCOL DATE: 3/28/19

Template Revised: June 14, 2010

- iii) Naturopathic medical students will come to the study area in groups of 15-25 (each naturopathic cohort will be studied on a different day)
- iv) Naturopathic medical students will be studied on the day of a classroom examination with three left arm seated blood pressure readings and one heart rate reading taken 15 minutes after the end of the exam and then 15 minutes after that.
- v) All participants will be instructed to download Headspace app onto their smartphone prior to the research date
- vi) The participants will be randomized into three groups
  - (1) Group I
    - (a) Baseline (15 minutes post-exam) blood pressure readings (three left arm seated readings, average will be calculated) and one heart rate reading taken after at least 5 minutes of rest time without talking, eating, or caffeine consumption.
    - (b) This group will not be given any intervention. Subjects will sit quietly for 15 minutes and can read a book, surf the internet, etc. Subjects may not consume caffeine, eat food, or listen to any meditation during this time.
    - (c) Three left arm seated blood pressure readings and one heart rate will be taken 15 minutes after the baseline reading.
  - (2) Group II
    - (a) Baseline (15 minutes post-exam) blood pressure readings (three left arm seated readings, average will be calculated) and one heart rate reading taken after at least 5 minutes of rest time without talking, eating food, or caffeine consumption.
    - (b) 15 minutes after classroom examination – will be given 1/4 tsp of blackstrap molasses placebo and a 10 minute audio-guided mobile meditation session via the Headspace App. Subjects may not consume caffeine or eat food during this time.
    - (c) Three left arm seated blood pressure readings and one heart rate will be taken 15 minutes after the baseline reading.
  - (3) Group III

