- i) [name] will evaluate the adverse events survey and follow up with any participant who experience a moderate-severe adverse event
  - ii) Participants will be encouraged to report additional adverse events to [name] directly in the days following the research even once the survey has been handed in.
- g) Withdrawal of subjects\***
- i) Participants can voluntarily withdraw at any time
  - ii) Once a participant has withdrawn from the research, his/her data will not be included in our analysis
  - iii) Withdrawal may occur without the participants' consent if:
    - (1) His/Her smartphone or Headspace application is not functioning within 30 minutes after the end of his/her classroom examination
    - (2) He/She did not take the classroom examination that day
    - (3) He/She eats food/tyramine containing food, stimulant medication, alcoholic beverages, cold medicine, decongestant medication, antihistamine medication, cough suppressant medication, stimulant energy drinks, or consume caffeine within 2 hours before the study period or during the study period.
- 7) Risks to subjects\***
- a) Privacy Risks**
- i) Since naturopathic medical students will be studied in groups in one large room, the subjects will be informed that his/her classmates in the same room will know that he/she is participating in the study.
  - b) To minimize any privacy risks, all medical information will be collected in private before the day of the study. On the day of the study, we will not read the participants' blood pressure and heart rate readings out loud. We also will ask the participant to write down what medications or drinks taken on the day of the study

UB HRP-503 TEMPLATE: Protocol

PROTOCOL TITLE: Investigating the short-term effects of *Passiflora incarnata* and mobile audio-guided meditation on blood pressure and heart rate in naturopathic medical students

PROTOCOL DATE: 3/28/19

Template Revised: June 14, 2010

so that the participant does not have to say this information out loud in order to protect privacy.

- c) **Inconveniences: Time Invested/Timing with Classroom Examination**
  - i) The participants may be inconvenienced by sparing 45 minutes after his/her classroom examination
  - ii) The participant may feel distracted during his/her examination in anticipation of the research taking place after the examination
    - (1) This is unlikely, as the research is intended to have a relaxing benefit on the participant

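### Section 6(g) drops participants withdrawn for app failure after randomisation, which would be expected mainly in Groups II and III, so contrasts with Group I carry an avoidable risk of bias whose size is unknown and may be zero

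*Protocol*

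**What the plan says.** The rule has two parts, both in Protocol section 6(g). The data rule, 6(g)(ii), is general: "Once a participant has withdrawn from the research, his/her data will not be included in our analysis". It does not separate voluntary withdrawal from withdrawal decided by the investigators. Section 6(g)(iii) then lists grounds on which withdrawal may, not must, occur without the participant's consent. The first is: "His/Her smartphone or Headspace application is not functioning within 30 minutes after the end of his/her classroom examination". The other two are not having sat the examination, and food, drink or medication intake in the 2 hours before or during the study period.

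On timing, section 6(d)(ii) says: "Students will be randomized to Group I, II, or III before the study begins". The app ground therefore acts after allocation.

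On who needs the app, section 6(b)(i)(1) requires it of all: "Participants must have a smartphone with access to the Headspace application and headphones to listen to the session". Section 6(d)(v) adds: "All participants will be instructed to download Headspace app onto their smartphone prior to the research date". Under section 6(d)(vi), however, only Groups II and III have the 10-minute Headspace session. Group I has no intervention, and its instruction reads: "Subjects may not consume caffeine, eat food, or listen to any meditation during this time".

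All three groups have a second set of readings 15 minutes after baseline, and taking them does not require a working app.

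**The concern.** An exclusion made after randomisation is harmless to a comparison only if it falls alike on the arms compared, or is unrelated to the outcome. Here the ground is failure of the tool that delivers an intervention given in two of the three arms. A Group I participant has no reason to open the app during the session, so a failure there would usually go unnoticed.

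This touches a stated aim. The hypothesis in section 2 is that "blood pressure levels and heart rates, as an assessment of sympathetic tone, will decrease significantly in response to both" the extract and the meditation. Groups II and III both meditate, so a meditation effect can be read only against Group I. Those are the exposed contrasts. If participants whose app fails tend to have a different change in blood pressure or heart rate, removing them from Group II while their counterparts stay in Group I shifts the estimated difference even when meditation does nothing. The exclusion is also unnecessary, because the outcome reading could still be taken.

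**Working it through.** **Reading the sections together.** Randomisation comes first (6(d)(ii)), the app ground acts later (6(g)(iii)(1)), and the data are then left out (6(g)(ii)). No other section restores analysis as randomised. App use is confined to Groups II and III (6(d)(vi)).

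**No plan figure to reproduce.** The protocol gives no expected rate of app failure and no effect size or SD. Section 6(b)(iv) supplies only the numbers of participants: "We aim for 70 subjects to participate but can complete the research with 45-60 subjects". With three equal arms (assumed, since no ratio is stated) this is 70/3 = about 23 per arm at the target and 45/3 = 15 at the minimum.

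**Assumptions, not in the protocol.** Let p be the share of Group II removed for app failure, taken as 5%, 10% or 20%. Let D be the mean change in removed minus retained participants, in SD units, taken as 0 to 1 in either direction. Group I loses nobody on this ground. The test is two-sided at 5%.

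**Bias.** With no true effect, the mean of a complete arm equals the retained mean plus p × D. Group I keeps that mean and Group II keeps the retained mean, so the bias has size p × D.

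**Type I error.** This is the rejection probability of a two-sample t test with noncentrality p × D / √(1/n + 1/(n(1−p))). For n = 23, p = 0.10 and D = 0.5:
- Group II retains 23 × 0.90 = 20.7
- the standard error is √(1/23 + 1/20.7) = 0.303
- the noncentrality is 0.05/0.303 = 0.165
- the rejection rate is 5.30%

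| Removed (p) | D (SD) | Bias (SD) | Type I error, 23 per arm | Type I error, 15 per arm |
|---|---|---|---|---|
| any | 0 | 0 | 5.00% | 5.00% |
| 5% | 0.25 | 0.0125 | 5.02% | 5.01% |
| 5% | 0.5 | 0.025 | 5.08% | 5.05% |
| 5% | 1 | 0.05 | 5.31% | 5.20% |
| 10% | 0.25 | 0.025 | 5.07% | 5.05% |
| 10% | 0.5 | 0.05 | 5.30% | 5.19% |
| 10% | 1 | 0.10 | 6.20% | 5.76% |
| 20% | 0.25 | 0.05 | 5.28% | 5.18% |
| 20% | 0.5 | 0.10 | 6.12% | 5.71% |
| 20% | 1 | 0.20 | 9.57% | 7.87% |

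**Check by simulation** (100,000 runs, with would-be failures present in Group I but kept). At p = 0.20 and D = 1, rejection was 9.04% with exclusion and 5.01% analysed as randomised for 23 per arm; for 15 per arm it was 7.26% and 4.98%. At p = 0.10 and D = 1 it was 6.00% and 4.95% (23 per arm), and 5.66% and 4.96% (15 per arm). Analysis as randomised restores the nominal level.

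**In students.** At 23 per arm, 5%, 10% and 20% removed is 1.2, 2.3 and 4.6 people. At 15 per arm it is 0.8, 1.5 and 3.0.

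**Separate timing check.** Section 6(d) places baseline at minute 15 after the examination and the second reading 15 minutes later: 15 + 15 = minute 30. The app limit in 6(g)(iii)(1) is also minute 30. On this nominal schedule, an app that starts working at the limit leaves no time for a 10-minute session before the second reading. Actual readings may run later (five cuffs and one pulse oximeter for 15-25 students, about 45 minutes in all), and nothing above depends on this point.

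**The case against.** The strongest reply is that arm dependence is inferred and not written. The app ground names no group, and everyone needs phone and app access and must download the app beforehand. It could be meant as a readiness check on all participants, and the eligibility checklist and app instructions (Attachments B and E) are not part of the text at hand. This stands in part, and it is why the exclusions are described as expected mainly, not only, in Groups II and III. The protocol text describes no check on the day in Group I, so the inference remains the natural one.

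Second, failures are probably few, given the eligibility rule, the advance download, the written instructions and the advice to use wifi. They may also be unrelated to blood pressure or heart rate. This stands in full and sets the size of the point.

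Third, a reader might infer that the contrast sets the whole of Group I against only those whose app worked. The protocol does not support that. Group I also loses voluntary withdrawals and those removed on the examination and intake grounds. App withdrawal is discretionary, so Groups II and III may retain some participants with failures.

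A missing analysis plan is no defence here, because the protocol itself fixes the exclusion.

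**Conclusion.** The point holds as a minor one. The protocol fixes a post-randomisation exclusion that would be expected to fall mainly on Groups II and III, and the contrasts with Group I are exposed to it. Group III versus II is largely unaffected because both groups use the app. The examination and intake grounds can arise in any group and, if applied evenly, are not part of this concern.

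A reader might infer a demonstrated bias or an invalid trial. The document supports neither: it does not link app failure to the outcomes, and neither size nor direction can be derived from it. Under the assumed rates, type I error stays at or below 5.3% for 5-10% removed with D up to 0.5 SD. It reaches about 7-10% only when failures are both common (20%) and strongly selective (1 SD). If D is zero there is no bias at any rate. No claim is made about loss of power.

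**What to change.** Keep section 6(g)(ii) for voluntary withdrawals and for grounds (iii)(2) and (iii)(3), and add one exception that separates a failed session from leaving the analysis:

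*A participant whose phone or app fails is not withdrawn from the analysis for that reason: the scheduled second reading is taken and the participant is analysed in the assigned group. An analysis without these participants is a sensitivity analysis. Withdrawals and app failures are reported by group and reason.*

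Alternatively, check app function in all participants before allocation. This makes the check the same for every group and avoids the dilution described below, although an app that passes could still fail later.

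The exception costs a few lines of text and a reading that is already scheduled. Its downside is dilution from incomplete sessions. If a failed session has none of the effect, the estimate shrinks by the factor 1 − p, to 95%, 90% or 80% of its value at 5%, 10% or 20% failure. The sensitivity analysis would show this.

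Separately, the 30-minute app limit in 6(g)(iii)(1) and the nominal reading times in 6(d) should be reconciled.

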**c) Study Endpoints\***

i) **Primary endpoints:** Blood pressure readings in mm/Hg and heart rate in beats per minute (bpm)

(1) According to the American Heart Association, blood pressure readings are as follows:

(a) Normal: Less than 120/80mmHg

(b) Elevated: 120-129/<80 mmHg

(c) Stage I Hypertension: 130-139/80-89 mmHg

(d) Stage II Hypertension: >140/>90 mmHg

(e) Hypertensive Crisis: >180/>120 mmHg

ii) **Primary safety endpoints:** Adverse events will be recorded for both *Passiflora incarnata* extract and the audio-guided meditation

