    - (a) Baseline (15 minutes post-exam) blood pressure readings (three left arm seated readings, average will be calculated) and one heart rate reading taken after at least 5 minutes of rest time without talking, eating, or caffeine consumption.
    - (b) 15 minutes after examination – will be given 1/8 tsp (900mg) of *Passiflora incarnata* solid extract by Wise Woman Herbals mixed with 1/8 tsp of blackstrap molasses to mask the taste and a 10 minute audio-guided mobile meditation session via the Headspace App. Subjects may not consume caffeine or eat food during this time.
    - (c) Three left arm seated blood pressure readings and one heart rate will be taken 15 minutes after the baseline reading.

UB HRP-503 TEMPLATE: Protocol

PROTOCOL TITLE: Investigating the short-term effects of *Passiflora incarnata* and mobile audio-guided meditation on blood pressure and heart rate in naturopathic medical students

PROTOCOL DATE: 3/28/19

Template Revised: June 14, 2010

vii) Safety considerations

- (1) All participants will be given a paper survey about adverse events (*see Attachment C*) which will be returned to the research team by the end of the same study day. Any participant who marks a moderate-severe adverse event will be followed up by [name] for appropriate management.
- (2) [name] phone number and contact information will be given to the study subjects so they can contact her in the event another adverse event arises after the survey has been returned.
- (3) The research will last for about 45 minutes. Three Blood pressure readings (all left arm seated) and one heart rate reading will be taken at baseline and again 15 minutes later.
- (4) Procedures taken to lessen the probability or magnitude of risks
  - (a) Adverse events related to *Passiflora incarnata* use have been found with chronic dosage. We attempt to minimize these risks by providing one-time acute dosage.
  - (b) We are attempting to minimize adverse events by excluding participants who are taking hypertensive medication, anti-anxiety medication, MAOI medication, or blood-thinning medication.
  - (c) We are attempting to minimize adverse events by excluding participants who are pregnant or may be pregnant.

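### The withdrawal rule in 6(g)(ii) has no exception for adverse events, so an event in a participant already dosed can be collected and managed but not counted in the primary safety endpoint

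*Protocol*

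**What the plan says.** All references are to the Protocol.

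- **Endpoint.** Section 6(c)(ii) sets the primary safety endpoint: "Adverse events will be recorded for both" the extract and the meditation.
- **Collection.** Section 6(d)(vii)(1): "All participants will be given a paper survey about adverse events", to be returned the same day, with follow-up of moderate to severe events. Section 6(f)(ii) adds: "Participants will be encouraged to report additional adverse events to" an investigator in the following days. Under 6(e)(iii) the survey carries the same participant code as the blood pressure and heart rate readings.
- **Withdrawal.** Section 6(g)(i): "Participants can voluntarily withdraw at any time". Section 6(g)(iii) also lets the investigators withdraw a participant without consent. One reason is "His/Her smartphone or Headspace application is not functioning within 30 minutes after the end of his/her classroom examination". Another is taking a listed item "within 2 hours before the study period or during the study period"; the list includes food, caffeine and antihistamines.
- **Consequence.** Section 6(g)(ii): "Once a participant has withdrawn from the research, his/her data will not be included in our analysis".

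No separate safety population is described. No sentence keeps a withdrawn participant's adverse events in the analysis.

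**The concern.** A safety endpoint normally counts everyone exposed, whatever happens afterwards. Here one unqualified sentence removes all data of anyone who withdraws, at whatever point and for whatever reason. A student who takes the preparation, feels unwell and leaves before the second reading is a voluntary withdrawal. The protocol provides for that student's care and survey, but not for the event appearing in the results.

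If people with an event are more likely to leave than people without one, the loss is related to the outcome and the reported rate is too low. Investigator-imposed withdrawals mostly do not have this link, but they still remove exposed people from the denominator, together with any events they had. With roughly 15 to 23 people per group, one lost record can decide whether an uncommon event is reported at all.

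This is not a detail left to an analysis plan. The protocol fixes the rule itself, and a plan that counted these events would contradict it.

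**Working it through.** **1. Can withdrawal follow dosing?** Group III receives the extract "15 minutes after examination" (6(d)(vi)(3)(b)), and Group II receives placebo at the same time. App failure is judged up to 30 minutes after the examination, which is up to 30 − 15 = 15 minutes after the dose. Consumption during the study period and voluntary withdrawal can also come after the dose. So all three routes can remove someone already exposed. One of them can be tied to an event: a dosed student who takes an antihistamine during the session for a reaction meets the wording of 6(g)(iii)(3).

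**2. Inputs.** The protocol gives no figure for this loss, so there is none to reproduce.

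- Group III size n: 70/3 ≈ 23 at the target, 60/3 = 20 and 45/3 = 15 at the stated minimum range (6(b)(iv)). Equal allocation is assumed because no ratio is given.
- Event rates p: dizziness 5% and allergy 2.5%, from the 260 mg dental extraction trial in section 3. Section 7(f) gives dizziness as up to 5%. Section 3 also cites a 500 mg study with no adverse events, so the range starts at zero. Applying these rates to the 900 mg used here is an assumption.
- Share w of affected participants who withdraw: not in the protocol. Assumed 10%, 25% and 50%.

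**3. Chance of losing at least one record.** A record is lost when a participant has the event and withdraws, with probability p·w. Treating participants as independent, P(at least one lost) = 1 − (1 − p·w)^n.

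| Event | n | w = 10% | w = 25% | w = 50% |
|---|---|---|---|---|
| Dizziness, 5% | 23 | 1 − 0.995^23 = 10.9% | 1 − 0.9875^23 = 25.1% | 1 − 0.975^23 = 44.1% |
| Dizziness, 5% | 20 | 9.5% | 22.2% | 39.7% |
| Dizziness, 5% | 15 | 7.2% | 17.2% | 31.6% |
| Allergy, 2.5% | 23 | 1 − 0.9975^23 = 5.6% | 1 − 0.99375^23 = 13.4% | 1 − 0.9875^23 = 25.1% |

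**4. Effect of losing one case.** If one of 23 is affected, the full report is 1/23 = 4.3%, with a Clopper-Pearson 95% interval of 0.1% to 21.9%. If that person is removed, the report is 0/22, with upper limit 1 − 0.025^(1/22) = 15.4%. The upper limit falls although information has been lost.

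**5. Effect on the rate of a common event.** If only affected participants withdraw, the reported rate is about (p − w·p)/(1 − w·p). Section 7(f) gives drowsiness as up to 50%. At p = 50%:

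- w = 10%: 0.45/0.95 = 47.4%
- w = 25%: 0.375/0.875 = 42.9%
- w = 50%: 0.25/0.75 = 33.3%

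At p = 20% (muscle relaxation, also given as an upper figure) the results are 18.4%, 15.8% and 11.1%. At p = 5% they are 4.5%, 3.8% and 2.6%.

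**The case against.** **The sentence may refer only to blood pressure and heart rate.** Section 6(e)(viii) gives the data analysis to the student assistants and an investigator, while sections 9 and 10 bar the assistants from the adverse event questionnaire. Section 6(f)(i) has adverse events evaluated separately. This reading is possible. But an investigator is also named as analyst, the survey carries the same code as the readings, and nothing in the text narrows the rule. Even on this reading the sentence needs a qualifier.

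**Few people will withdraw after dosing.** The final reading is 15 minutes after baseline. Someone whose symptoms start later has already finished the measurements and has little left to withdraw from. Withdrawal under 6(g)(iii) is discretionary, and its listed reasons are not themselves adverse events. This stands. It keeps the likely effect small, and it means the calculation, which applies whole-study event rates to a short window, leans high.

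**A stronger reading is tempting.** The chance that at least one of 23 has dizziness is 1 − 0.95^23 = 69%, and for allergy 1 − 0.975^23 = 44%. A reader might take these as the chance that safety data are lost. They are the chance that an event occurs; loss also requires that the affected person withdraws, and the documents do not say how often that would happen. Nor do they show that the rule would produce a report free of events. At a 20% rate of muscle relaxation the chance of no case in 23 is 0.8^23 = 0.6%.

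**Conclusion.** The rule is too broad as written. Taken literally, it drops adverse events of dosed participants from the primary safety endpoint, and any event-driven withdrawal would push the reported rate down. The defect lies in the analysis; collection and care are provided for.

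The size is uncertain and probably small. With 23 in Group III and 10% to 50% of affected students withdrawing, the chance of losing at least one record is about 11% to 44% for dizziness and about 6% to 25% for allergy. These figures rest on equal allocation, on rates from a single 260 mg trial, and on an assumed withdrawal share. That events would prompt withdrawal is a reasonable inference; the protocol does not state it.

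A reader might conclude that the rule could reverse the trial's safety conclusion. The documents do not support that. They set no safety hypothesis, threshold or decision rule, and the intervals for 1/23 and 0/22 largely overlap. What can change is whether an uncommon event is reported once or not at all. That justifies a short correction.

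**What to change.** - Limit 6(g)(ii) to the analysis of blood pressure and heart rate.
- State that the safety endpoint counts every participant who received the extract or placebo, or started the meditation, grouped by what was received, whether or not they later withdrew. Include events reported up to withdrawal, and later ones where the participant agrees.
- Offer the existing Attachment C survey to anyone leaving early, and record the reason for leaving.
- Check that the consent form agrees with this. It was not available for review, so whether it already does cannot be judged. A participant would remain free to decline further data collection.

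The cost is one or two sentences in the protocol, a matching line in the consent form if it is missing, and possibly a slightly less favourable adverse event rate. No dose, schedule or clinical rule changes.
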